#### **Within the TP53 WT population**

- To compare the proportions of *complete remission (CR)* between treatment arms
- To compare event-free survival (EFS) between treatment arms
- *To compare ORR (defined as CR), complete remission with incomplete platelet count recovery [CRp], and complete remission with incomplete blood count recovery [CRi] between treatment arms*
- *To compare duration of remission following CR (DOR) between treatment arms*
- To compare the proportions of allogeneic HSCT following CR between treatment arms
- *To assess OS and CR in clinically actionable mutation-defined AML subpopulations, including FLT3, IDH1, and IDH2*
- *To assess the safety of idasanutlin plus cytarabine as compared with cytarabine and placebo*
- *To compare the differences in disease and treatment-related symptoms and health-related quality of life between treatment arms*

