#### **4.5.12 Patient-Reported Outcomes**

PRO data will be collected via electronic questionnaires to more fully characterize the clinical profile of idasanutlin. The questionnaires will be translated as required in the local language. To ensure instrument validity and that data standards meet health authority requirements, questionnaires scheduled for administration during a clinic visit should be completed prior to the performance of non-PRO assessments and the administration of study medication.

The EORTC QLQ-C30 is a validated and reliable self-reporting measure (Fayers et al. 2001) consisting of 30 questions incorporated into five functional scales (physical, role, cognitive, emotional, and social), three symptom scales (fatigue, pain, nausea, and vomiting), and a global health status/global quality-of-life scale. The remaining single items (dyspnea, appetite loss, sleep disturbance, constipation, and diarrhea) assess the additional symptoms experienced by patients with cancer and the perceived financial burden of treatment. The EORTC QLQ-C30 questionnaire takes 5 minutes to complete. The EORTC QLQ-C30 will be conducted using electronic patient-reported outcome (ePRO) prior to treatment across all cycles on Days 1, 8, 15, and 28, and between Days 29–56, if applicable. Additionally, the EORTC QLQ-C30 will be collected during study drug completion/discontinuation visit and every 3 months until relapse during long-term follow-up of patients in clinical remission. An additional EORTC QLQ-C30 questionnaire must also be completed after progressive disease (PD).

The EQ-5D-5L is a self-report health status questionnaire that consists of six questions used to calculate a health utility score for use in health economic analysis (EuroQol Group 1990; Brooks 1996; Herdman et al. 2011; Janssen et al. 2013). There are two components to the EQ-5D-5L: a five-item health state profile that assesses mobility, self-care, usual activities, pain/discomfort, and anxiety/depression, as well as a visual analogue scale that measures overall health state. Published weighting systems allow for creation of a single summary score. Overall scores range from 0 to 1, with low scores representing a higher level of dysfunction. The EQ-5D-5L questionnaire takes

5 minutes or less to complete, and assessments are made at the same time as the EORTC QLQ-C30. An additional EQ-5D-5L questionnaire is also required to be completed after PD.

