### **4.8 PATIENT-REPORTED OUTCOMES**

The PRO-evaluable population will include all randomized patients who have a baseline and at least one post-baseline PRO assessment. The PRO-evaluable population will be used for descriptive analyses of visit summary and change from baseline, and responder analyses. All TP53 WT randomized patients will be used for completion analyses and time-to-event (improvement/deterioration) analyses. All PRO analyses will be performed based on the treatment arm assigned at randomization.

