For physical function and global health status/QoL, higher scores are reflective of better HRQoL and a clinically meaningful improvement is defined as at least a 10-point increase. For fatigue, lower scores are reflective of less fatigue and a clinically meaningful improvement is defined as at least a 10-point decrease. Conversely, clinically meaningful deterioration is defined as at least a 10-point decrease and 10-point increase, respectively.

Time to deterioration is defined as the time from randomization to the first documentation of a 10-point decrease in EORTC QLQ-C30 physical functioning and global health status and a 10-point increase in fatigue from baseline. Time to

improvement is defined as the time from randomization to the first documentation of a 10-point increase in EORTC QLQ-C30 physical functioning and global health status and a 10-point decrease in fatigue from baseline.

Time to deterioration and time to improvement will be displayed using Kaplan Meier curves. Patients who do not have an observed deterioration or improvement, respectively, at the time of clinical data cut-off will be censored at the last non-missing assessment date. Patients without a post-baseline assessment will be censored at randomization.

The EQ-5D-5L questionnaire consists of two components: the EQ-5D-5L descriptive system, which has 5 dimensions (mobility, self-care, usual activities, pain/discomfort, and anxiety/depression) with five levels (no problems, slight problems, moderate problems, severe problems, and extreme problems) and a visual analogue scale (EQ VAS) ranging from 0 (worst possible health state) to 100 (best possible health state), which measures an overall health state.

The EQ-5D-5L health states, which are defined based on the EQ-5D-5L descriptive system, will be converted into a single index value according to the EQ-5D-5L guidelines ([van Reene and Janssen 2015](#)). The EQ-5D-5L single index value will be calculated using the United Kingdom preference weights. Descriptive statistics (mean, standard deviation, median, minimum, and maximum) and change from baseline will be presented by treatment arm and at each timepoint.

Data from the EQ-VAS will be used to assess the overall health status. Descriptive statistics (mean, standard deviation, median, minimum, and maximum) and change from baseline at each timepoint will be displayed by treatment arm.

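### PRO time-to-event curves censor deaths, so they overstate improvement and deterioration by about 1 to 6 points at Day 56, and each quality-of-life objective gets only part of the PRO analyses

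*SAP*

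**What the plan says.** Protocol 2.2 sets quality of life as a secondary objective within the TP53 WT population: "To compare the differences in disease and treatment-related symptoms and health-related quality of life between treatment arms". It sets the same comparison again, as a separate objective, within all patients.

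SAP 4.8 divides the analyses. "The PRO-evaluable population will include all randomized patients who have a baseline and at least one post-baseline PRO assessment"; that set, which is not limited by TP53 status, carries the visit summaries, change from baseline and responder analyses. "All TP53 WT randomized patients will be used for completion analyses and time-to-event (improvement/deterioration) analyses".

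SAP 4.8.1 defines the events by a 10-point change alone: "Time to deterioration is defined as the time from randomization to the first documentation of a 10-point decrease" on the functioning and global health scales, or a 10-point rise in fatigue; improvement is the mirror image. Patients with neither, as applicable, "at the time of clinical data cut-off will be censored at the last non-missing assessment date", and "Patients without a post-baseline assessment will be censored at randomization". "Time to deterioration and time to improvement will be displayed using Kaplan Meier curves"; no test, hazard ratio or cumulative incidence is specified.

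Under Protocol 4.5.12, forms are due on Days 1, 8, 15 and 28 of each cycle, once more between Days 29 and 56 where applicable, and at the discontinuation visit. After that they are due "every 3 months until relapse during long-term follow-up of patients in clinical remission", plus one form after progressive disease.

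**The concern.** Death is neither an event, nor a competing event, nor a separate category in SAP 4.8.1, so deaths without a prior 10-point change fall under the general censoring rule. Kaplan-Meier then treats those patients as if they could still improve or deteriorate at the same rate as the living. With planned median survival of 6 and 9 months, deaths in the PRO window are common, and under the alternative hypothesis they differ by arm. The curves would then overstate both probabilities, somewhat more in the arm with more deaths.

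The population split is a separate matter. Each objective is served by only some of the analyses, and the completion rates (TP53 WT) describe a different population from the means and responder proportions they are meant to qualify (all randomized patients with evaluable forms).

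**Working it through.** **Does another section repair either point?** No.
- SAP 4.10 refers PRO missing-data rules back to 4.8.
- The drop-out-as-event sensitivity analyses in SAP 4.4.3 cover OS and EFS only.
- The competing-risk analysis in SAP 4.9 covers cause of death only.
- SAP 4.9 repeats the primary and secondary efficacy endpoints in all patients, but SAP 2.2.2 does not list PROs among these.
- SAP 4 says in general terms that the main comparison is in TP53 WT and in all randomized patients, but 4.8 is more specific.

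**Survival model.** The documents give no PRO event rates, so the check starts from their survival model (Protocol 6.1 and 6.11.1): CR 16% vs 32.3%, half of CRs long-term survivors (taken here as no deaths), control medians 5.1 months (non-responders) and 7.5 months (short-term responders), and hazard ratio 0.8 in both groups. The idasanutlin medians are then 5.1/0.8 = 6.375 and 7.5/0.8 = 9.375 months.

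S(t) = (1 − p)·2^(−t/m1) + (p/2)·2^(−t/m2) + p/2

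This returns the planned medians: S(6) = 0.498 for control and S(9) = 0.499 for idasanutlin. Simulating the model to 275 events gives 85.5% power against the stated 85%.

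**Deaths by Day 56** (56/30.4375 = 1.84 months):
- Control: 0.84 × 0.7788 + 0.08 × 0.8436 + 0.08 = 0.802, so 19.8% dead.
- Idasanutlin: 0.677 × 0.8187 + 0.1615 × 0.8728 + 0.1615 = 0.857, so 14.3% dead.

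**Overstatement to Day 56.** Assume a constant PRO hazard h, equal in both arms and independent of death. Kaplan-Meier with deaths censored targets 1 − exp(−h × 1.84). The probability of actually having the event is the integral of h·exp(−ht)·S(t) from 0 to 1.84.

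| h per month (assumed) | 1 − KM, either arm | Cumulative incidence, control | Cumulative incidence, idasanutlin | Overstatement, control / idasanutlin (points) |
|---|---|---|---|---|
| 0.05 | 8.79% | 7.89% | 8.15% | 0.9 / 0.6 |
| 0.1 | 16.81% | 15.12% | 15.60% | 1.7 / 1.2 |
| 0.2 | 30.79% | 27.80% | 28.65% | 3.0 / 2.1 |
| 0.4 | 52.09% | 47.35% | 48.70% | 4.7 / 3.4 |

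At 0.2 per month the arms differ by about 1 point in cumulative incidence (28.65 − 27.80 = 0.85) and not at all in 1 − KM.

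**Check on a form schedule.** A simulation used forms at Days 8, 15, 28, 42 and 56, exponential death with medians of 6 and 9 months, an assumed median time to a 10-point change of 1.5, 3 or 6 months, with and without a shared frailty. The overstatement was about 2 to 6 points in control and 1 to 4 with idasanutlin. Patients dead by Day 56 with no recorded change, hence censored, were 12 to 18% vs 8 to 12%. In the 3-month, no-frailty case (control vs idasanutlin):
- 1 − KM: 34.7% vs 34.6%
- cumulative incidence: 30.8% vs 32.0%
- deterioration-or-death: 47.1% vs 43.3%

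**Population split.**

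| Analysis | TP53 WT objective | All-patient objective |
|---|---|---|
| Visit summary, change from baseline, responders | not planned | planned, PRO-evaluable patients only |
| Completion, time to event | planned | not planned |

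Protocol 6.1 expects 374 of 440 patients to be TP53 WT, so about 66 (15%) of those randomized would be mutant.

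**The case against.** The strongest defence is that censoring at death still yields a legitimate cause-specific quantity. If the arms have equal hazards of improvement, overlapping Kaplan-Meier curves show that correctly, and the gap in cumulative incidence comes from survival. This stands: the error lies in reading 1 − KM as a probability, which is how a displayed curve is usually read.

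The consequences are also limited. The curves are descriptive, PROs are outside the fixed testing sequence in SAP 4.4.2, and deaths are reported as OS and as 30- and 60-day mortality. A reader might infer that early deaths are hidden from the trial; they are not. They are only absent from these curves, and patients who recorded a deterioration before dying do count as events.

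A reader might also extend the calculation to month 6, where a hazard of 0.2 per month gives 1 − KM of 70% against cumulative incidences of 54% and 58%. The documents do not support that use. It assumes everyone is observed continuously for six months, whereas regular follow-up forms continue only for patients in remission. A non-responder whose last form was near Day 56 and who dies in month 5 was not censored because of death.

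Finally, it might be inferred that neither objective is answered at all. That is too strong. The all-patient objective still receives change from baseline on all scales, responder proportions with confidence intervals and EQ-5D-5L summaries, and the TP53 WT objective receives completion and time-to-event displays. No effect of the split on any result has been quantified.

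**Conclusion.** Both points hold, at moderate importance. As written, 1 − KM overstates the probability of improvement or deterioration by about 1 to 5 points in control and 1 to 3 with idasanutlin to Day 56 (2 to 6 and 1 to 4 in the simulated form schedule). The sizes rest on the plan's survival assumptions and on assumed PRO hazards that are equal in both arms; the direction does not depend on the hazards chosen. Informative censoring is wider than death, because treatment failure and relapse also end regular PRO collection.

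The population split follows from the text without any assumption: each objective lacks part of the PRO analyses, and completion is reported in a different population from the means.

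**What to change.** **SAP 4.8.1.** State how death is handled. Present time to improvement and time to deterioration as cumulative incidence with death as a competing event, counting deaths up to a stated window after the last scheduled form. Keep the Kaplan-Meier curves, labelled as cause-specific displays. Add deterioration-or-death as a supportive composite, with a note that it may largely track OS. State that censoring at treatment failure or relapse remains informative and that the competing-event analysis does not remove it.

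**SAP 4.8.** Run completion, visit summary, change from baseline, responder and time-to-event analyses in TP53 WT patients for that objective, and repeat the set in all randomized patients for the other.

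**Cost.** SAP wording and additional tables. Survival status and questionnaires are already collected, and SAP 4.9 already plans cumulative incidence methods for cause of death. Reported improvement rates will be slightly lower.

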#### **4.9 EXPLORATORY ANALYSES**

Primary and secondary efficacy endpoints will be repeated for the all-patient-ITT population using the same methods as described for the TP53 WT population.

Rate of CRMRD will be analysed using same methods as CR.

CR during treatment will be analysed using the same methods as for CR.

Proportion of HSCT *following response* (OR) and HSCT regardless of response will be analysed using the same methods as HSCT following CR.

LFS (Duration of OR) will be analysed using the same methods as DOR.

Depending on the number of patients, exploratory analyses might be performed to assess the possible relationship between idasanutlin consolidation therapy in Cycle 2 and Cycle 3 and the time-to-event measures (OS, EFS, DOR).

Depending on the number of patients who undergo allogeneic HSCT, a landmark OS analysis will be performed with the date of HSCT as baseline using the same methods as for the primary OS endpoint. In addition, a comparison of patients between treatment groups with a similar level of response (i.e., CR, CRi, and CRp) proceeding to transplant or not, might be assessed to describe if there is a difference on their survival outcome.

As a supportive analysis, a competing risk analysis of cause-specific death (with event types "death due to progression of disease" and "death due to adverse event or other reasons") as an exploratory analysis will be performed including the following:

- A visualization of the corresponding cumulative incidence functions
- A cause-specific hazard and Fine-Gray regression models for the competing events

with randomized treatment assignment as the main covariate and potential adjustment for additional potential prognostic variables.

Additional biomarker analyses might be performed as appropriate.

#### **4.10 MISSING DATA**

The missing data rules for the primary and secondary efficacy endpoints and for PROs are detailed in Sections 4.4 and 4.8, respectively.

For the reporting of safety data, the following missing data imputation rules will be applied:

- Adverse events with missing grades will be included in the summaries as Grade 3–5 adverse events.
- Adverse events with missing relationship to trial medication will be included in the summaries of treatment related adverse events.
- Adverse events with missing seriousness will be included in all summaries of serious adverse events.

In case of missing day in a time-to-event-date, an imputation is done on the first day of the month or date of randomization, whichever occurs last; otherwise no imputations are performed for the main analysis.

In case of missing assessment of patient primary population (i.e. wild type status), according to FMI an imputation may be done depending on availability of alternative data by Almac, as specified in Section 4.4

Specific sensitivity analyses are going to be performed on missing data as specified in Section 4.4.3.

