## Follow-Up

Patients in CR/CRp/CRi after terminating study treatment will be followed for EFS, *DOR*, and *LFS*. HMRA will be performed monthly ( $\pm 5$  days) until disease progression/relapse is noted or until the patient moves to HSCT. Every 3 months HMRA will include assessment of bone marrow aspirate; in all other instances, HMRA will be based on peripheral blood counts only.

In the event of relapse, a HMRA based on a bone marrow aspirate is required. In addition, whole blood in EDTA for biomarker analysis should be obtained.

For patients who move to HSCT, an HMRA based on a bone marrow aspirate should be performed to document the bone marrow status prior to the start of conditioning therapy. The quantity of the bone marrow aspirate should also allow for exploratory biomarker analyses (MRD/Flow, EDTA, and Paxgene), and the hematopoietic cell transplantation-specific comorbidity index (HCT-CI) score (Sorrer et al. 2005; Sorror 2013) should be obtained to document the patient's health status prior to the start of conditioning therapy.

All patients will be followed every 3 months for study treatment-related serious adverse events, fatal adverse events, subsequent anti-cancer therapies, and survival status. Survival follow-up ends with death or end of study. Adverse events should be followed as outlined in Section 5.3.1 and Section 5.6. Please see [Appendix 1](#) for the schedule of follow-up assessments.

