In case disease progression/relapse is determined solely by symptomatic deterioration or by a hematology assessment, a bone marrow aspirate should be performed at that

time to complete HMRA. If a patient progresses/relapses outside of the scheduled visit, an unscheduled HMRA must be provided.

If a bone marrow aspirate is performed at any unscheduled timepoint while on study, an unscheduled HMRA must be provided.

Please note that at the time of bone marrow sampling for HMRA the bone marrow sample collected (aspirate) should also allow for exploratory analyses (MRD by flow cytometry, EDTA, Paxgene) and amount taken should be taken into consideration (Section 4.5.10.6).

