## **2.2 OUTCOME MEASURES**

### **2.2.1 Primary Efficacy Outcome Measures**

The primary endpoint for this study is OS in the TP53 WT population. OS is defined as the time from randomization to death from any cause. OS for patients who have not died at the time of the analysis will be censored at the last date the patient was known to be alive.

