### **2.2.2 Secondary Efficacy Outcome Measures**

The secondary efficacy outcome measures for this study are as follows, for the TP53 WT population:

- CR is defined as a complete remission as reported by the investigator over the induction cycle (Cycle 1).
- EFS is defined as the time from the date of randomization to treatment failure (failure to achieve CR, set as day of final response assessment), relapse from CR, or death from any cause, whichever occurs first. Patients with no EFS event will be censored at the date of last response assessment (pre-HSCT) or last date known to be alive (post-HSCT). Patients with no EFS event and no post-baseline response assessment will be censored at date of randomization.
- Overall remission (ORR; CR, CRp, and complete remission with incomplete blood count recovery [CRi]) over the induction cycle (Cycle 1)
- DOR (or Duration of CR) is defined only for patients who achieve a CR and is measured from the date of achievement of CR until the date of relapse from CR, or death from any cause. Patients who do not have a DOR event will be

censored the date of last response assessment (pre-HSCT) or last known alive date (post-HSCT).

- The proportion of HSCT following a CR is defined as proportion of patients undergoing allogeneic HSCT following the corresponding CR
- CR in clinically actionable mutation defined subpopulations (FLT3, IDH1 and IDH2)
- OS in clinically actionable mutation defined subpopulations (FLT3, IDH1 and IDH2)

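### The rule for a missing event day uses randomization as its only floor, so it can date a death before a documented alive date, or a relapse or death before the remission it follows

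*SAP*

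**What the plan says.** SAP 4.10 gives one rule for a time-to-event date that lacks its day: "an imputation is done on the first day of the month or date of randomization, whichever occurs last". It allows nothing further: "otherwise no imputations are performed for the main analysis". For efficacy it also points elsewhere: "The missing data rules for the primary and secondary efficacy endpoints and for PROs are detailed in Sections 4.4 and 4.8, respectively". Section 4.4 has no partial-date rule, and the sensitivity analyses in 4.4.3 deal with loss to follow-up, stopped assessments, new therapy and transplant, not with incomplete dates. The protocol has no partial-date rule either.

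The plan uses the two other relevant dates for different purposes. The last alive date is a censoring date: under SAP 2.2.1, OS for patients who have not died "will be censored at the last date the patient was known to be alive". The date of CR is a time origin: under SAP 2.2.2, DOR "is measured from the date of achievement of CR until the date of relapse from CR, or death from any cause". LFS (SAP 2.2.4) is built the same way from any remission. Neither date serves as a lower bound for an imputed event.

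**The concern.** Randomization protects the imputed date only when the event falls in the month of randomization. In any later month the rule returns the first of that month, even where the database shows the patient alive, or entering remission, later in the same month.

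Two kinds of error follow. In OS and EFS, a death can be dated before a visit that the patient attended, and in EFS a relapse can precede the CR it ends. In DOR and LFS, where the clock starts at remission, the time can be zero or negative. The SAP does not say how such a time is handled. If that is left to programming, a patient may be dropped without a pre-specified reason. DOR is fourth in the fixed testing sequence of SAP 4.4.2, so it is a formally tested endpoint.

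**Working it through.** No figure in the plan depends on this rule, so there is nothing to reproduce. The check applies the rule to dates.

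**Rule.** Imputed date = max(first of the recorded month, randomization date).

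**Examples**, with randomization on 10 January of a non-leap year:

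- *Death.* Last documented alive 20 June; died 25 June, day missing. Imputed death = max(1 June, 10 January) = 1 June, 19 days before the patient was documented alive. OS is 142 days, against 161 days to last contact and 166 to the true death.
- *Relapse.* CR on 7 March (day 56 after randomization); relapse 30 March, day missing. Imputed relapse = 1 March, so DOR = 1 March − 7 March = −6 days. EFS is 50 days: positive, but it ends before the CR at 56 days. A death on 30 March with a missing day gives the same DOR of −6.

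The randomization floor acts in neither example.

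**Size of the shift.** Assume event days spread evenly over the year and the floor not acting. The mean of (day of month − 1) is 15 in a 31-day month, 14.5 in a 30-day month and 13.5 in February:

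(7 × 31 × 15 + 4 × 30 × 14.5 + 28 × 13.5) / 365 = 5,373 / 365 = 14.7 days, maximum 30.

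A simulation of 400,000 dates over three years gave the same 14.7.

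**How often the order is reversed, among events with a missing day.** The gaps are assumptions; the documents do not give them.

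| Deaths: last contact uniformly within | Imputed before last contact | Mean shift, present rule | Mean shift, last alive date as floor |
|---|---|---|---|
| 7 days | 84% | 14.7 days | 3.6 days |
| 30 days | 46% | 14.7 days | 10.1 days |
| 91 days | 15% | 14.7 days | 13.2 days |

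| Relapse after CR by | Imputed strictly before CR |
|---|---|
| 7 days | 74% |
| 14 days | 51% |
| 21 days | 28% |
| 28 days | 5% |
| 30 days or more | 0% |

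The 28-day row can be checked by hand. Relapse must fall on the 30th or 31st, which is 2 days in each of 7 months and 1 day in each of 4, so 18/365 = 4.9%.

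**Size of the DOR set.** From SAP 2.3: 374 *TP53* WT patients, 2:1, CR 32.3% and 16%. That gives 374 × 2/3 × 0.323 ≈ 80 and 374 × 1/3 × 0.16 ≈ 20 patients with CR. One bad or dropped time would be visible in a set of 20.

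**The case against.** The strongest reply is that few dates will be affected. In remission, "HMRA will be performed monthly" (Protocol 4.5.2, Follow-Up), and Protocol 4.5.8 adds: "If a patient progresses/relapses outside of the scheduled visit, an unscheduled HMRA must be provided". A relapse is confirmed on bone marrow, which is a dated procedure, so a relapse with no day should be uncommon. With monthly assessment, CR and relapse will seldom share a calendar month. Fatal adverse events are reportable within 24 hours (Protocol 5.4), and data are queried and source-verified (Protocol 7.1 and 7.4). A missing day of death is most plausible in the three-monthly survival follow-up, where the 15% row applies rather than the 84% row. All of this stands as an argument about frequency. It does not make the rule correct for the dates it does touch.

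It is also fair to say that first, middle or end of month are all conventions. Moving a date earlier is therefore not an error in itself; contradicting a recorded later date is.

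A reader might infer two stronger points, and the documents support neither:

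- *That OS or EFS times can be negative.* Both clocks start at randomization, and the rule floors the event there.
- *That the primary analysis is materially biased, for instance by about 8% of the six-month control median (15/183).* That ratio compares one patient's shift with a median; it is not the effect on the median. If 1% to 10% of death dates lacked a day (an assumption), the mean shift over all deaths would be 0.01 × 14.7 ≈ 0.15 to 0.10 × 14.7 ≈ 1.5 days. The rule is the same in both arms of a blinded trial, and no effect on the log-rank test or hazard ratio is shown.

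**Conclusion.** The point holds as a minor fault in a stated rule. Followed exactly, SAP 4.10 can produce event dates that contradict the trial's own records, and zero or negative times in DOR and LFS. Each affected date moves earlier by about 15 days on average and 30 at most, assuming event days spread evenly within the month. The death conflict arises whenever the last contact falls after the first of the month of death. The relapse conflict needs remission and relapse in one calendar month and should be rarer; a death with a missing day soon after remission is a second route to the same result.

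The number of partial dates is unknown, the treatment of the arms is symmetric, and the event count, alpha and power figures are untouched. The overall effect is probably small. The case for changing the text is that the rule gives dates known to be wrong, and that SAP Version 3 lists more precise handling of missing data among its aims.

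**What to change.** Amend the rule in SAP 4.10 so that a missing day is imputed to the latest of:

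- the first of the recorded month;
- the date of randomization;
- for deaths, the last documented date on which the patient was alive;
- for relapse or death in DOR and LFS, and for relapse in EFS, the date of the remission concerned.

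Including EFS in the last item ensures that one relapse carries one date in every endpoint. Do not add a day to any floor. With a last alive date of 30 June and a death recorded in June, an added day would give 1 July, outside the recorded month, and would rule out death on the day of last contact.

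In the examples above, the death becomes 20 June, and the relapse becomes 7 March with DOR = 0 and EFS = 56 days. Reversed orderings disappear by construction. Because a zero time remains possible, the SAP should say how it enters the DOR and LFS analyses. It should also define the last documented alive date for patients who died, since the plan now uses that date only for censoring. A sensitivity analysis with mid- or end-of-month dates would be a simple addition.

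The cost is a few sentences in the SAP, using dates that the trial already collects. They are best settled before any unblinded OS analysis.
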